9.3 Clinical Study Report and Publications

A Signatory Investigator must be selected to sign the clinical study report.

For this protocol, the Signatory Investigator will be selected as appropriate based on the following criteria:

- External Principal Investigator designated at protocol development.

The data collected during this study are confidential and proprietary to BMS. Any publications or abstracts arising from this study require approval by BMS prior to publication or presentation and must adhere to BMS's publication requirements as set forth in the approved clinical trial agreement (CTA). All draft publications, including abstracts or detailed summaries of any proposed presentations, must be submitted to BMS at the earliest practicable time for review, but at any event not less than 30 days before submission or presentation unless otherwise set forth in the CTA. BMS shall have the right to delete any confidential or proprietary information contained in any proposed presentation or abstract and may delay publication for up to 60 days for purposes of filing a patent application.

10 GLOSSARY OF TERMS

Term	Definition
Complete Abstinence	
If one form of contraception is required, Complete Abstinence is defined as complete avoidance of heterosexual intercourse and is an acceptable form of contraception for all study drugs. Female subjects must continue to have pregnancy tests. Acceptable alternate methods of highly effective contraception must be discussed in the event that the subject chooses to forego complete abstinence.
 
If two forms of contraception is required, Complete abstinence is defined as complete avoidance of heterosexual intercourse and is an acceptable form of contraception for all study drugs. Subjects who choose complete abstinence are not required to use a second method of contraception, but female subjects must continue to have pregnancy tests. Acceptable alternate methods of highly effective contraception must be discussed in the event that the subject chooses to forego complete abstinence.
 
Expanded definition Complete abstinence as defined as complete avoidance of heterosexual intercourse is an acceptable form of contraception for all study drugs. This also means that abstinence is the preferred and usual lifestyle of the patient. This does not mean periodic abstinence (eg, calendar, ovulation, symptothermal, profession of abstinence for entry into a clinical trial, post-ovulation methods) and withdrawal, which are not acceptable methods of contraception. Subjects who choose complete abstinence are not required to use a second method of contraception, but female subjects must continue to have pregnancy tests. Acceptable alternate methods of highly effective contraception must be discussed in the event that the subject chooses to forego complete abstinence

11 LIST OF ABBREVIATIONS

Term	Definition
AE	adverse event
AI	accumulation index
AI_AUC	AUC Accumulation Index; ratio of AUC(TAU) at steady state to AUC(TAU) after the first dose
AI_Cmax	Cmax Accumulation Index; ratio of Cmax at steady state to Cmax after the first dose
ALT	alanine aminotransferase
ANC	absolute neutrophil count
ANOVA	analysis of variance
aPTT	activated partial thromboplastin time
AST	aspartate aminotransferase
AT	aminotransaminases
AUC	area under the concentration-time curve
A-V	atrioventricular
β -HCG	beta-human chorionic gonadotrophin
BMI	body mass index
BMS	Bristol-Myers Squibb
BP	blood pressure
C	Celsius
C12	concentration at 12 hours
C24	concentration at 24 hours
Ca ⁺⁺	calcium
CBC	complete blood count
CBR	Clinical benefit ratio
CFR	Code of Federal Regulations
CI	confidence interval
Cl ⁻	chloride
CLcr	creatinine clearance
CLR	renal clearance
CLT	total body clearance

Term	Definition
cm	centimeter
C _{max} , C _{MAX}	maximum observed concentration
C _{min} , C _{MIN}	trough observed concentration
CNS	Central nervous system
CRF	Case Report Form, paper or electronic
C _{trough}	Trough observed plasma concentration
CV	coefficient of variation
CYP	cytochrome p-450
D/C	discontinue
dL	deciliter
ECG	electrocardiogram
eCRF	Electronic Case Report Form
EDC	Electronic Data Capture
EEG	electroencephalogram
eg	exempli gratia (for example)
ESR	Expedited Safety Report
FDA	Food and Drug Administration
FSH	follicle stimulating hormone
g	gram
GCP	Good Clinical Practice
GGT	gamma-glutamyl transferase
GFR	glomerular filtration rate
h	hour
HBsAg	hepatitis B surface antigen
HBV	hepatitis B virus
HCV	hepatitis C virus
HCO ₃ ⁻	bicarbonate
HIV	Human Immunodeficiency Virus
HR	heart rate
HRT	hormone replacement therapy

Term	Definition
ICD	International Classification of Diseases
ICH	International Conference on Harmonisation
ie	id est (that is)
IEC	Independent Ethics Committee
IMP	investigational medicinal products
IND	Investigational New Drug Exemption
IRB	Institutional Review Board
IU	International Unit
IV	intravenous
K ⁺	potassium
kg	kilogram
L	liter
LD	longest dimension
LDH	lactate dehydrogenase
ln	natural logarithm
mg	milligram
Mg ⁺⁺	magnesium
MIC	minimum inhibitory concentration
min	minute
mL	milliliter
mmHg	millimeters of mercury
MS	mass spectrometry
MTD	maximum tolerated dose
µg	microgram
N	number of subjects or observations
Na ⁺	sodium
N/A	not applicable
ng	nanogram
NIMP	non-investigational medicinal products
NSAID	nonsteroidal anti-inflammatory drug

Term	Definition
OS	Overall survival
PD	pharmacodynamics
PK	pharmacokinetics
PO	per os (by mouth route of administration)
PT	prothrombin time
PTT	partial thromboplastin time
QC	quality control
QD, qd	quaque die, once daily
RBC	red blood cell
SAE	serious adverse event
SD	standard deviation
SOP	Standard Operating Procedures
sp.	species
Subj	subject
t	temperature
T	time
TID, tid	ter in die, three times a day
WBC	white blood cell
WHO	World Health Organization
WOCBP	women of childbearing potential
x g	times gravity

APPENDIX 2 ECOG

ECOG PERFORMANCE STATUS*	
Grade	ECOG
0	Fully active, able to carry on all pre-disease performance without restriction
1	Restricted in physically strenuous activity but ambulatory and able to carry out work of a light or sedentary nature, e.g., light house work, office work
2	Ambulatory and capable of all selfcare but unable to carry out any work activities. Up and about more than 50% of waking hours
3	Capable of only limited selfcare, confined to bed or chair more than 50% of waking hours
4	Completely disabled. Cannot carry on any selfcare. Totally confined to bed or chair
5	Dead

2.3	03Dec2020		Document history: Additional clarification of the reasoning for the update of section 4.1 on 23Apr2020. Section 1: Added information about eligibility for enrollment of symptomatic subjects. Section 3.1 and 4.1: Time period of SD is corrected to ≥ 6 months. Section 4.1: Added clarification of subsequent anti-cancer therapy. Section 4.2: Overall survival (OS) is added to the list of secondary endpoints Section 7.5.1: Added methodology for CRB based on BOR as reported on CRF. Section 7.5.5.2: Added clarification for concordance tables. Appendix 1: Updated Table 11-3 - Select Adverse Events Minor editorial corrections.

TABLE 1: ABBREVIATION

AE	Adverse Event
ALT	Alanine Aminotransferase
ANOVA	Analysis of Variance
AST	Aspartate Aminotransferase
BICR	Blinded Independent Central Review
BMS	Bristol-Myers Squibb
BMI	Body Mass Index
BOR	Best Overall Response
BUN	Blood Urea Nitrogen
CBR	Clinical Benefit Rate
CI	Confidence Interval
CNS	Central Nervous System
CR	Complete Response
CRF	Case Report Form, Paper or Electronic
CSR	Clinical Study Report
CTC	Common Toxicity Criteria
DOR	Duration of Response
ECG	Electrocardiogram
ECOG	Eastern Cooperative Oncology Group
eg	Exempli Gratia (for example)
HBV sAG	Hepatitis B surface antigen
HBV	Hepatitis B virus
HCRU	Healthcare Resource Utilization
HCV	Hepatitis C Virus
HCV RNA	Hepatitis C Virus Ribonucleic Acid
ie	Id Est (That Is)
IV	Intravenous
IVRS	Interactive Voice Response System
kg	Kilogram
LDH	Lactate Dehydrogenase
MDSC	Myeloid-Derived Suppressor Cells
MedDRA	Medical Dictionary for Regulatory Activities
mg	Milligram

MRI	Magnetic Resonance Imaging
N	Number of Subjects or Observations
NANO	Neurologic Assessment in Neuro-Oncology
NCI CTCAE	National Cancer Institute's Common Toxicity Criteria for Adverse Events
NSCLC	Non-small Cell Lung Cancer
OS	Overall Survival
ORR	Objective Response Rate
PD	Progressive Disease
PFS	Progression Free Survival
PO	Per os (by mouth route of administration)
PPD	Pharmaceutical Product Development, LLC
PR	Partial Response
PT	Preferred Terms
Q2W	Every 2 Weeks
Q3W	Every 3 Weeks
QD	Quaque Die, Once Daily
RECIST	Response Evaluation Criteria in Solid Tumors
SAE	Serious Adverse Event
SAP	Statistical Analysis Plan
SD	Stable Disease
SOC	System Organ Class
SRT	Stereotactic Radiotherapy
TSH	Thyroid-stimulating Hormone
TTR	Time to Objective Response
ULN	Upper Limit Normal
UTD	Unable to Determine
WHO	World Health Organization

Research Hypothesis:

Treatment with nivolumab combined with ipilimumab, followed by nivolumab monotherapy, will provide clinical benefit to subjects with melanoma metastatic to the brain.

Schedule of Analyses:

The first interim analysis was conducted after 20 subjects have completed induction treatment or have been discontinued due to an Adverse Event (AE) or progression after treatment with at least one dose of combination treatment.

After the first interim safety analysis conducted by the steering committee, the combination was determined to be safe in patients with asymptomatic untreated melanoma intracranial metastases. Per Amendment 02 (August 2016), the patient population will be expanded to include Cohort B that will enroll approximately 20 patients.

The final analysis will be performed following the data base lock after all subjects have completed the study. Study schedules are detailed in protocol Section 5.1.

2 STUDY DESCRIPTION

2.1 Study Design

This is an open-label, multi-site Phase 2 study of nivolumab combined with ipilimumab followed by nivolumab monotherapy for the treatment of subjects with melanoma metastatic to the brain. Cohort A comprises subjects with histologically confirmed metastatic melanoma presenting with intracranial metastases and at least 1 measurable index intracranial metastasis ≥ 0.5 cm and ≤ 3 cm in diameter that has not been previously irradiated. No clinical requirement for local intervention (surgery, radiosurgery, corticosteroid therapy) or other systemic therapy. Per Amendment 02, August 2016, the patient population was expanded to include Cohort B, which will enroll approximately 20 patients with histologically confirmed metastatic melanoma presenting with symptomatic intracranial metastases who may be on steroids with doses no higher than a total daily dose of 4 mg of dexamethasone or equivalent that is stable or tapering within 10 days prior to treatment. Patients who are symptomatic and are not being treated with steroids are also eligible for Cohort B. Patients enrolled in Cohort B must have at least 1 measurable index intracranial metastasis ≥ 0.5 cm and ≤ 3 cm in diameter that has not been previously irradiated, must not require immediate local therapy (SRT or surgery within 3 weeks prior to first treatment), performance status must be 0-2, and no experience of seizure within 10 days prior to first treatment. Asymptomatic subject who are enrolling into Cohort A and become symptomatic during the screening evaluations may be considered for enrollment into Cohort B if they meet all other criteria

for Cohort B. No crossover between cohorts is permitted after the start of treatment. Subjects with a history of whole brain irradiation are not eligible for this study.

All patients will be treated with the combination regimen of nivolumab 1 mg/kg combined with ipilimumab 3mg/kg Q3W (4 doses) followed by nivolumab monotherapy (3 mg/kg Q2W) for a maximum of 24 months, or until disease progression or unacceptable toxicity or withdrawal of consent.

[figure not shown]
The combination induction regimen of nivolumab and ipilimumab followed by nivolumab maintenance monotherapy proposed for this study is based on safety and tolerability data from the use of nivolumab and ipilimumab in systemic metastatic melanoma and other tumor types (Protocol Section 1.4.3) and the proposed treatment regimen is expected to be tolerable in subjects with melanoma metastatic to the brain.

The use of SRT for a single episode of disease progression for ≤ 3 intracranial lesions is permitted (Protocol Section 3.4.2.2). Recommended intervals between treatment with study drug and use of SRT, dose delay after SRT, allowable steroid use (≤ 16 mg dexamethasone PO QD), and tapered over no more than 4 weeks), and observation of patients post SRT when treatment is resumed are also specified in Section 3.4.2.2. Any subject who meets criteria for discontinuation following SRT (Protocol Section 4.5.5) will proceed to follow-up for safety, progression, and overall survival (OS) after discontinuation of study medication based on the assessment schedules presented in Protocol Section 5.

To assess safety and tolerability as well as efficacy, one interim analysis was conducted for this study after 20 subjects completed induction treatment or had discontinued treatment for any reason. At the completion of the interim analysis by the steering committee, the study drug treatment was deemed as safe in asymptomatic patients. A second cohort of patients who are symptomatic will be enrolled per Amendment 02 (August 2016). The study will close after the last enrolled subject completes 5 years of follow up from the date of first treatment.

The study design schematic is presented in Figure 1.

Figure 1: Study Design Schematic

1 Subjects may continue to receive treatment for a maximum of 24 months, or until confirmed progression or unacceptable toxicity or patient withdrawal of consent. After discontinuation from treatment with study drug(s) subjects will proceed to follow-up. Subjects who continue to respond at the end of on study treatment may be prescribed study medication through commercial supply or appropriate standard of care per investigator.

2 Use of SRT for progression of ≤ 3 intracranial lesions will be allowed per protocol-specific guidelines. Subjects who require SRT for a second episode of disease progression will be discontinued from treatment and proceed to follow-up.

3 All subjects who are discontinued from treatment with study drug(s) or received a maximum of 24 months of treatment will proceed to follow-up.

This study will consist of three phases: screening, treatment, and follow-up. And the treatment phase has two parts: Part I – Induction, Part II – Maintenance.

2.2 Treatment Assignment

CA209204 study is an open-label study. After the subject's initial eligibility is established and informed consent has been obtained, the subject must be enrolled into the study by calling an interactive voice response system (IVRS) to obtain the subject number. Every subject that signs the informed consent form must be assigned a subject number in IVRS. Specific instructions for using IVRS will be provided to the investigational site in a separate document.

All enrolled subjects will be treated in an open-label fashion as described below:

- Nivolumab administered IV over 60 minutes \pm 10 minutes at 1 mg/kg combined with ipilimumab administered IV over 90 minutes \pm 10 minutes at 3 mg/kg every 3 weeks for a total of 4 doses of the combination therapy followed by nivolumab administered IV over

60 minutes \pm 10 minutes at 3mg/kg every 2 weeks for a maximum of 24 months or until progression or unacceptable toxicity.

- Dose reductions or dose escalations are not permitted.
- Dose can be delayed for all drug-related adverse events (regardless of whether or not the event is attributed to nivolumab, ipilimumab, or both). All study drugs must be delayed until treatment can resume.
- If treatment is delayed $>$ 6 weeks, the subject must be permanently discontinued from study therapy, except as specified in protocol Section 4.5.2.1 and Section 4.5.5.
- If a patient requires SRT for a single episode of intracranial progression in \leq 3 intracranial metastases, treatment with study drug will be interrupted as specified in protocol Section 3.4.2.2.
- The protocol specified steroid treatment and taper (\leq 16 mg dexamethasone PO daily tapered in \leq 4 weeks four week steroid) must be completed before treatment with the study drugs is resumed.

2.3 Protocol Amendments

Global Amendment 03 (See Protocol Document History).

3 OBJECTIVES

Study objectives will be applied for all subjects (Cohort A and Cohort B).

Primary, secondary, and exploratory efficacy endpoints and safety analyses will be reported in the treated subjects, for overall population, by cohorts (asymptomatic and symptomatic), and by SRT status (prior to study with or without SRT and on study with or without SRT).

3.1 Primary Objective

The primary objective of this study is to assess intracranial clinical benefit rate (CBR, defined as complete response [CR] + partial response [PR] + stable disease [SD] \geq 6 months) in subjects with melanoma metastatic to the brain per modified RECIST 1.1 criteria.

3.2 Secondary Objective

The secondary objectives of this study are:

- To assess the extracranial clinical benefit rate defined as CR+PR+SD \geq 6 months (per RECIST 1.1 criteria)
- To assess intracranial objective response rate (ORR), intracranial progression-free survival (PFS) per modified RECIST 1.1 criteria
- To assess extracranial ORR, extracranial PFS per RECIST 1.1 criteria

4 ENDPOINTS

4.1 Primary Endpoints

The primary endpoint is intracranial CBR. It is defined as the proportion of all treated subjects whose best overall response (BOR) is either a CR or PR or whose BOR was SD with duration of ≥ 6 months, as determined by modified RECIST 1.1 criteria for index intracranial lesions based on investigator review.

The BOR is defined as the best response designation recorded between the date of first study dosing date and the date of progression, or the date of subsequent anticancer therapy (including tumor-directed radiotherapy and tumor-directed surgery), whichever occurs first. In this study, BOR is specified for the intracranial, extracranial, and global compartments based on the (1) modified RECIST 1.1 criteria (intracranial), (2) RECIST 1.1 criteria (extracranial), (3) combination of modified RECIST 1.1 criteria and RECIST 1.1 criteria (global). Best response determination in trials where confirmation of complete or partial response is required: Complete or partial responses may be claimed only if the criteria for each are met at a subsequent time point as specified in protocol Appendix 3. There is no confirmation requirement for progressive disease (PD). The BOR for each patient as determined by the BICR is determined from a predefined set of rules specified within the Image Review Charter.

To ensure the accuracy of primary endpoints, analyses will be based on two sets of BOR: BOR as reported in the CRF and BOR with adjustment. BOR as reported in the CRF uses information entered in the CRF directly by investigators without adjustment. Results based on BOR with adjustments will serve as primary analysis. This decision was made after the interim database lock on 09 August 2020.

BOR with adjustment uses information entered in the CRF with the following adjustments:

- If BOR is NE, and the radiographic progression date is non-missing and prior to subsequent anti-cancer therapy start date, or subsequent anti-cancer therapy start date is missing, change BOR to PD.
- If BOR is SD, and the radiographic progression date is non-missing and duration of SD is less than 6 months and radiographic progression date is prior to subsequent anti-cancer therapy start date, or subsequent anti-cancer therapy start date is missing, change BOR to PD.
- If BOR is PR or CR, and there is preceding (confirmed or unconfirmed) PD and
 - if the radiographic progression date is prior to or equal to the minimum of complete response date and partial response date, change BOR to PD;
 - if BOR is CR and both the complete response date and partial response date are non-missing and radiographic progression date is between those two, change BOR to PR.

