All patients will be treated with the combination regimen of nivolumab 1 mg/kg combined with ipilimumab 3 mg/kg Q3W (4 doses), followed by nivolumab monotherapy (3 mg/kg Q2W) for a maximum of 24 months, or until disease progression or unacceptable toxicity. The use of SRT (single episode) for disease progression for ≤ 3 intracranial lesions is permitted. (Section 3.4.2.2) Recommended intervals between treatment with study drug and use of SRT, dose delay after SRT, allowable steroid use (≤ 16 mg dexamethasone PO QD), and tapered over no more than 4 weeks), and observation of patients post SRT when treatment is resumed are also specified in Section 3.4.2.2. Any subject who meets criteria for discontinuation following SRT (Section 4.5.5) will proceed to follow-up for safety, progression, and overall survival after discontinuation of study medication based on the assessment schedules presented in Section 5. NOTE: To continue on-study after SRT, at least 1 non-irradiated target lesion must remain after SRT treatment.

A follow-up period of 3 years from the date of first treatment with study drugs is available for all subjects. The study will close after the last enrolled subject completes 3 years of follow up from

the date of first treatment or the study is discontinued by the Sponsor. The study design is presented in [Figure 3.1-1](#):

Figure 3.1-1: CA209204 Study Design

- Subjects may continue to receive treatment for a maximum of 24 months, or until confirmed progression or unacceptable toxicity. After discontinuation from treatment with study drug(s) subjects will proceed to follow-up. Subjects who continue to respond at the end of on study treatment may be prescribed study medication through commercial supply or appropriate care per investigator.
- Use of SRT for progression of ≤ 3 intracranial lesions will be allowed per protocol-specific guidelines (See Section 3.4.2.2). Subjects who require SRT after second episode of disease progression will be discontinued from treatment and proceed to follow-up.
- All subjects who are discontinued from treatment with study drug(s) will proceed to follow-up. See Table 5.1-4 for schedule of follow up assessments.

SRT = stereotactic radiotherapy

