4.5.2.2 Resumption of Treatment after Dose Delay

If there is a delay in treatment due to AEs associated with study medication, when the patient resumes treatment, he/she will receive the next dose, rather than the missed dose. If the dose delay occurs during the combination treatment (induction), the patient will receive less than 4 doses of the combination treatment.

If there is a delay due to SRT or AEs not associated with study medication, when the patient resumes treatment, he/she will receive the missed dose. If the dose delay occurs during the combination treatment (induction), the patient has the opportunity to receive all four doses of the combination treatment.

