7.5.2.8 Progression Free Survival

The intracranial, extracranial and global PFS will be estimated using the Kaplan-Meier product-limit method, together with a two-sided 95% confidence interval for the median, calculated using the method of Brookmeyer and Crowley method.

PFS rates at 6, 12, 18, 24, 36, 48 months, and then every year will be estimated using KM estimates on the PFS curve. Minimum follow-up must be longer than the timepoint to generate the rate. Associated two-sided 95% CIs will be calculated. Results will be tabulated and plotted.

The source of progression event (death versus progression) will be summarized.

The status of subjects who are censored in the PFS KM analysis will be tabulated using the following categories:

- On-study (on-treatment, in follow-up)
- Off-study (lost to follow-up, withdrawn consent, never treated)
- Received subsequent anticancer therapy

All PFS data will be listed. In addition, a listing of subjects who were treated beyond progression will also be presented.

Sensitivity analyses using BICR-assessed PFS (intracranial, extracranial, and global) will also be performed for the above analyses and BICR PFS data will be listed.

In addition, to assess consistency of treatment effect in PFS in different subgroups, a ‘forest’ plot of the PFS rate at 6 month and two-sided 95% CIs based on Kaplan-Meier estimates will be produced on intracranial, extracranial and global PFS for the same variables as in section 7.5.2.2.

Primary censoring rules for the analysis of PFS are presented in Table 7.5.2.8-1.

Table 7.5.2.8-1: Censoring Scheme for Primary Definition of PFS

Situation	Date of Progression or Censoring	Outcome
No baseline tumor assessment	Date of first study treatment	Censored
No on-study tumor assessments and no death	Date of first study treatment	Censored
Documented progression	Date of first documented progression per RECIST 1.1 (excludes clinical progression)	Progressed
No progression and no death	Date of last evaluable tumor assessment	Censored
New anticancer therapy, tumor-directed radiotherapy, or tumor-directed surgery received without progression reported prior or on the same day	Date of last evaluable tumor assessment prior to initiation of subsequent therapy	Censored
Death without progression	Date of death	Progressed

[REDACTED]

In addition, a categorical summary of DOR will be presented for intracranial, extracranial and

[REDACTED]

[REDACTED]

[REDACTED]

[REDACTED]

[REDACTED]

[REDACTED]

[REDACTED]

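### Read literally, the one permitted course of brain SRT ends the extracranial response window and censors extracranial PFS with no extracranial event

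*SAP*

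**What the plan says.** **Response window.** SAP 4.1 ends the best-overall-response (BOR) window at progression "or the date of subsequent anticancer therapy (including tumor-directed radiotherapy and tumor-directed surgery), whichever occurs first". The next sentence there says that "BOR is specified for the intracranial, extracranial, and global compartments", with no separate window for each. Protocol 8.4.2 has the same rule. Protocol 8.3.1.1 refers to subsequent therapy without naming radiotherapy.

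**PFS.** SAP 7.5.2.8 gives one censoring table for intracranial, extracranial and global PFS. One row covers "New anticancer therapy, tumor-directed radiotherapy, or tumor-directed surgery received without progression reported prior or on the same day", and the censoring date is "Date of last evaluable tumor assessment prior to initiation of subsequent therapy".

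**Permitted SRT.** SAP 2.1 states: "The use of SRT for a single episode of disease progression for ≤ 3 intracranial lesions is permitted". Under Protocol 4.5.2.2, after a delay for SRT, "when the patient resumes treatment, he/she will receive the missed dose". Protocol 3.1 adds: "To continue on-study after SRT, at least 1 non-irradiated target lesion must remain after SRT treatment". Protocol 5.4 continues scans until progression or the end of treatment, whichever is later.

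**Where SRT is set apart.** SAP 7.2.2 names it as permitted when defining protocol deviations. Neither the BOR window nor the censoring table repeats this, and SAP 7.5.2.7 lists radiotherapy under subsequent therapy.

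**Reporting.** SAP 3 has efficacy reported "by SRT status (prior to study with or without SRT and on study with or without SRT"). The analysis excluding on-study SRT (SAP 7.5.1, Protocol 8.5.2) covers intracranial CBR only.

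**The concern.** A subject can have stable extracranial disease, progress in the brain, receive the permitted SRT, resume study drug and continue to be scanned. The extracranial data exist, yet a literal reading of the window discards everything after SRT. Stable disease can then never reach 6 months if SRT came earlier, and a partial response not yet confirmed is lost. Extracranial rates use all treated subjects as the denominator, so such a subject counts as a failure. In PFS the same subject is censored because of brain progression. That censoring is informative if brain and extracranial progression tend to occur together.

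At stake are the secondary extracranial estimates and their breakdown by on-study SRT. No planned extracranial analysis would show how much of the result comes from the rule.

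**Working it through.** **1. What the rules give under each reading.** The text leaves two things open: whether SRT given between study doses is *subsequent* therapy, and which compartment's progression counts.

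| Reading | Extracranial BOR window | Extracranial PFS |
|---|---|---|
| SRT counts; progression is compartment-specific | Closes at SRT | Censored at last scan before SRT |
| Progression in any compartment counts | Closes at brain progression | Censoring row not triggered, because progression was already reported |
| SRT is not subsequent therapy | Stays open | Not censored, although the row names radiotherapy |

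SAP 4.2 ties extracranial endpoints to RECIST 1.1 and intracranial ones to the modified criteria. That favours compartment-specific progression, so the first reading is sized below.

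For intracranial endpoints, permitted SRT follows brain progression, which has normally closed the window already. The same holds for global endpoints.

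**2. The plan's own figure.** SAP Table 5-1 plans extracranial (and global) CBR at 65/110 = 59.1%. Clopper-Pearson gives a 90% CI of 50.8% to 67.0% and a 95% CI of 49.3% to 68.4%, both as stated.

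**3. Effect on extracranial CBR.** Let p = 65/110 = 0.591. Let s be the share of subjects with on-study SRT. Let f be the share of their extracranial benefit lost because SRT came before it qualified. The documents give neither s nor f, so both are assumed. SRT subjects are taken to have the planning benefit rate.

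Loss = p × s × f. Remaining benefit cases = 65 × (1 − s × f), rounded to whole subjects.

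| s | f | Loss (points) | Remaining cases | CBR |
|---|---|---|---|---|
| 5% | 25% | 59.1 × 0.05 × 0.25 = 0.7 | 64/110 | 58.2% |
| 10% | 25% | 59.1 × 0.10 × 0.25 = 1.5 | 63/110 | 57.3% |
| 5% | 100% | 59.1 × 0.05 = 3.0 | 62/110 | 56.4% |
| 10% | 100% | 59.1 × 0.10 = 5.9 | 59/110 | 53.6% |
| 15% | 100% | 59.1 × 0.15 = 8.9 | 55/110 | 50.0% |

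In whole subjects the loss is 0.9 to 1.8 points at f = 25% with s of 5% to 10%. It is 2.7 to 9.1 points at f = 100% with s of 5% to 15%.

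A single lost case (64/110) moves the exact 90% lower bound from 50.8% to 49.9%, below the 50% benchmark. The planned interval for extracranial CBR is 95% (SAP 7.5.2.1), and its lower bound at 65/110 is already 49.3%. This shows sensitivity and is not a changed decision.

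**4. Effect on extracranial PFS.** Exponential times to extracranial progression (true 6-month PFS 60%) and to SRT were simulated in 200,000 subjects, linked by a Gaussian copula with correlation ρ. Subjects were censored at SRT.

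| ρ | SRT by 6 months 10% | SRT by 6 months 20% |
|---|---|---|
| 0 | 60.1% | 59.9% |
| 0.3 | 61.1% | 62.0% |
| 0.6 | 61.8% | 63.6% |

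There is no bias under independence, and an upward bias of about 1 to 4 points under positive correlation. The simulation ignores scan spacing and the step back to the last scan before SRT.

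**The case against.** **The literal reading may not be the intended one.** Permitted SRT is given within study treatment, SAP 7.2.2 treats it as allowed, and a non-irradiated target lesion must remain, which suggests that response assessment goes on. The BOR adjustments in SAP 4.1 start from the investigator's CRF entry and use the therapy date only in turning NE or SD into PD. None of them truncates response at SRT. Protocol 3.4.2.2 and the response criteria in Appendix 3 are not in the public text and could settle the matter. This objection stands against treating truncation as certain. It does not remove the problem, because the visible text allows three different extracranial results.

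**A larger effect is tempting.** A reader might equate the assumed 5% to 15% SRT share with a loss of 5 to 15 points. That needs every SRT subject to have been a benefit case whose benefit had not yet qualified. Some Cohort A subjects have no measurable extracranial disease, and benefit established before SRT still counts.

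**The subgroup.** A reader might infer that the rule is what makes extracranial results with and without on-study SRT non-comparable, and that it lowers all of them. On-study SRT status is defined after baseline by brain progression, so the groups are not comparable under any window rule. For PFS the likely bias is upward.

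**Changing the main rule now.** Ending response at new therapy is a conservative convention. The current SAP (December 2020) postdates the August 2020 interim lock in an open-label, single-arm trial. Exempting SRT in the main analysis could only raise extracranial CBR and ORR. This stands, and it argues for reporting both versions.

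**Conclusion.** The point holds in limited form. With compartment-specific progression, SAP 4.1 and Table 7.5.2.8-1 let the permitted brain SRT end the extracranial BOR window and censor extracranial PFS without an extracranial event. No planned analysis shows the effect.

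Extracranial CBR can be biased down by about 3 to 9 points at most for assumed SRT rates of 5% to 15%. The bias is 1 to 2 points if a quarter of the benefit is lost at 5% to 10% SRT. ORR is biased in the same direction but was not sized. Extracranial PFS at 6 months may be biased up by about 0 to 4 points, depending on a correlation that the documents do not give.

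A reader might conclude that the overall extracranial results are driven by brain events. The documents do not support that: no SRT frequency is given, subjects without SRT are unaffected by this rule, and responses or progressions recorded before SRT still count. The primary intracranial endpoint is largely untouched.

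**What to change.** - In SAP 4.1 and Table 7.5.2.8-1, state that progression means progression in the compartment being analysed.
- In the same places, state whether the single permitted brain SRT counts as subsequent therapy for extracranial BOR, CBR, ORR and PFS.
- Extend the SRT sensitivity analysis in SAP 7.5.1 and 7.5.2 to extracranial CBR, ORR and PFS. Report each with and without brain-only SRT closing the window or censoring.
- Label the change as made after the interim lock.
- Leave the global endpoints unchanged.
- Present extracranial results by on-study SRT status as descriptive only.

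The cost is a few sentences and one extra run on scans the protocol already provides for. The downside is that, in the version ignoring SRT, any effect of SRT outside its field is credited to study drug. Showing both versions side by side makes the size of the difference visible.
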